12.2.2. Definitions of Severity

Adverse events will be graded using the CTCAE v.4.0 [USDHHS 2009].

Note that “seriousness” and “severity” are distinct concepts. “Serious” is a term applied to an AE that meets specific requirements (refer to Section 12.2.1). “Severity” refers to the AE intensity classification.

12.2.3. Relationship to Study Drug

The Investigator will determine the assessment of the causal relationship of the AE to the study drug.

The relationship of AEs to study drug is categorized as probable, possible, unlikely, or not related. An alternative etiology must be provided for all AEs for which the relationship to study drug is considered “possible,” “unlikely,” or “not related.”

Definitions of each of these terms are below:

Probable: The AE has a timely relationship to administration of the study drug and there is no apparent, potential alternate etiology.

Possible: The AE has a timely relationship to administration of the study drug and there is an apparent, potential alternate etiology.

Unlikely: The AE is likely related to an etiology other than administration of study drug.

Not Related: The AE is related to an etiology other than the study drug.

An AE with causal relationship not initially determined will require follow-up to assign causality.

12.2.4. Assessment of the Clinical Outcome of Adverse Events

The Investigator (a study physician) will determine the clinical outcome of the AE as follows:

Recovered Completely: Patient has fully recovered from the event with no residual effects observable.

Recovered with Sequelae: Effects of the event are stabilized and constant. The likelihood of these effects changing (improving or worsening) is low.

Not Yet Recovered: Effects of the event are still present and changing. The event is not considered recovered completely or recovered with sequelae.

CONFIDENTIAL

No use, disclosure or reproduction outside of Omeros without prior written authorization

Unknown; Lost to Follow-up: Not known, not observed, not recorded, or refused to provide information.

Died: The event may or may not be the primary cause of death (may or may not be the immediate cause of death).

12.3. Reporting Adverse Events

12.3.1. Adverse Event Reporting

Adverse events will be collected from the time informed consent is obtained until the last Follow-up visit.

All AEs will be documented in the source records and will be recorded in the CRFs as appropriate. All AEs, whether observed by the Investigator or reported by the patient, and whether or not thought to be related to the study drug, will be recorded on the appropriate CRF. In describing AEs on the CRF, standard, medically accepted terminology will be used.

The description of each AE will identify the date of onset, duration, severity (see Section 12.2.2 for Definitions of Severity), any action taken (including any diagnostic procedures or laboratory tests performed and all treatments that were administered), the outcome of the event, and relationship to the study drug.

Any medical condition that is present at the time that the patient is screened should be considered as baseline and not recorded as an AE. However, if the medical condition increases in frequency or severity during or following administration of the study drug, it will be recorded as an AE on the appropriate CRF.

An AE is defined as any untoward medical occurrence in a patient administered a pharmaceutical product and which does not necessarily have to have a causal relationship with this treatment. Adverse events may be reported by the patient, discovered by the Investigator and Investigator's staff, or detected through physical examination, laboratory test, or other means.

Adverse events include:

- Any unfavorable and unintended sign, medical diagnosis, or symptom that occurs between the time of the first administration of study drug and the study duration required by the protocol.
- Any new undesirable medical experience or an unfavorable and unintended change of an existing condition that occurs between the time of the first administration of study drug and the study duration required by the protocol, whether or not considered related to study drug.
- Abnormal laboratory findings considered by the Investigator to be clinically significant, i.e., those that are unusual for the population being studied or individual patient.

Whenever possible, the Investigator should group signs or symptoms that constitute a single diagnosis into a single event term. For example, cough, rhinitis, and sneezing might be grouped together as *upper respiratory tract infection*.

CONFIDENTIAL

No use, disclosure or reproduction outside of Omeros without prior written authorization

In cases where the Investigator notices an unanticipated benefit to the patient, study site personnel should enter *unanticipated benefit* with the actual event term (for example, the complete actual term may be *unanticipated benefit-sleeping longer*).

12.3.2. Serious Adverse Event Reporting

All SAEs will be:

- recorded on the appropriate SAE case report form
- followed through resolution or at a stable condition by a study physician
- reviewed by a study physician.

The investigative site is required to report any SAE directly to the Sponsor's pharmacovigilance designee on the Serious Adverse Event form within 24 hours of becoming aware of the event, whether or not the SAE is deemed drug-related (see Section 1.2 for contact information).

The study physician will complete an Expedited or Serious Adverse Event Form within the following timelines:

- All deaths and immediately life-threatening events, whether related or unrelated to study drug, will be recorded on the Expedited or Serious Adverse Event Form and faxed/electronically communicated within 24 hours of site awareness.

Other supporting documentation of the event may be requested by the pharmacovigilance staff and should be provided as soon as possible.

A distinction is drawn between serious and severe events. A severe event is a major experience of its type. A severe event does not necessarily need to be serious. For example, nausea that persists for several hours may be considered severe nausea, but not a serious adverse experience. On the other hand, a stroke that results in only a limited degree of disability may be considered a mild stroke, but it would be considered a SAE.

Death is an outcome of an event and not an event per se (sudden death or death of unexplainable causes can be reported, but follow-up will be required until cause of death is determined).

12.3.3. Reporting of Serious Adverse Events to Regulatory Agencies

The Sponsor or its designee will submit the SAEs requiring expedited reporting to regulatory agencies. The ethics committee will be notified of SAEs in accordance with federal, national, and local laws and regulations.

12.3.4. Pregnancy and Overdose Reporting

Cases of pregnancy must be reported for tracking purposes. If a patient becomes pregnant during the study, the Sponsor's Pharmacovigilance designee must be notified by fax or email within 24 hours of site awareness and the patient discontinued from study drug. Additional instructions for reporting of the pregnancy and outcome will be provided by the Sponsor at the time of notification. Pregnancies of partners of male patients will also be followed provided the patient's partner provides informed consent for follow-up of the pregnancy.

CONFIDENTIAL

No use, disclosure or reproduction outside of Omeros without prior written authorization

Occurrences of overdose should be reported to the Sponsor for tracking purposes. Overdose is defined as any dosing above the protocol-defined dosing instructions. Additional instructions for reporting overdose information will be provided by the Sponsor at the time of notification.

12.4. Type and Duration of the Follow-Up of Patients After Adverse Events

All reportable AEs will be followed until satisfactory resolution or until the Investigator deems the event to be chronic or the participant to be stable.

If an SAE persists at the last visit or the time of early termination after study treatment, it will be marked as “ongoing” and “not yet recovered” in the CRF. It will be followed by the Investigator until such time that it is deemed to be resolved or at a stable condition. Follow-up data for such SAEs will be collected in the source documents and reported appropriately.

12.5. Appropriateness of Measurements

12.5.1. Efficacy Measures

The primary efficacy measure evaluates the proportion of patients who respond to OMS721 treatment. The response criteria include laboratory measures of TMA activity and clinical status. These measures provide an assessment of underlying TMA activity as well as potential clinical benefit experienced by patients. Secondary efficacy measures provide population-level support for patient-level responses observed.

12.5.2. Pharmacokinetic Measures

Drug concentrations are standard PK measures.

12.5.3. Pharmacodynamic Measures

Inhibition of *ex vivo* lectin pathway activation is a relevant PD measure as this is the biological target of OMS721.

12.5.4. Immunogenicity Measures

Anti-drug antibody response is a standard immunogenicity measure for a therapeutic protein.

12.5.5. Exploratory Measures

Mannan-binding lectin and MASP-2 concentrations are being measured to assess whether OMS721 administration alters them. Laboratory TMA measures in patients with aHUS and TTP are appropriate exploratory evaluations in these populations.

12.5.6. Safety Measures

The collection of AEs, clinical laboratory tests, vital signs, and ECGs are standard safety measures.

13. STATISTICS

13.1. Determination of Sample Size

In Stage 1 of the study, 3 patients per dose escalation cohort is a common scheme and is considered to be sufficient in combination with data from the Phase 1 study to allow selection of a dose for Stage 2.

In Stage 2, the sample size for each cohort (aHUS and HSCT-TMA/TTP) is determined by comparison to the total sample size of uncontrolled Phase 2 studies that provided sufficient data for approval of eculizumab for the treatment of aHUS [Legendre 2013]. This sample size is considered adequate in these orphan diseases to identify treatment effects in uncontrolled studies.

It is expected that approximately 28 HSCT-TMA patients enrolled before Protocol Amendment 11 will be included to support a regulatory approval. The width of the exact 95% confidence interval (CI) for the response rate based on 28 HSCT-TMA patients ranges from 12.3% to 38.7%. If the observed response rate is 50%, the exact 95% CI is 30.6% to 69.4%.

Because this is an exploratory study, the sample size may be adjusted based on emerging data. If the sample size differs markedly from the planned enrollment, the protocol will be amended to accommodate the change.

13.2. Statistical and Analytical Plans

The statistical and analytical plans presented below are an overview of key analysis methods. Details of the analysis will be specified in the statistical analysis plan (SAP). A change to the data analysis methods described in the protocol will require a protocol amendment only if it alters a principal feature of the protocol. The SAP will be finalized prior to interim database lock. Any changes to the methods described in the final SAP will be described and justified in the clinical study report.

13.2.1. General Considerations

All data summaries will be descriptive in nature. Summary statistics for continuous variables will include number of patients, mean, median, standard deviation, minimum, and maximum. For categorical variables, frequencies and percentages will be provided. When required for the statistical analysis of a particular variable, the baseline value will be the last recorded value prior to the administration of the first dose of study treatment. There are 2 exceptions. The baseline platelet count is defined as the average of the 2 predose values. The baseline creatinine is defined as the maximum creatinine value between the diagnosis of TMA and 4 weeks after the first dose of OMS721.

Statistical analyses will be focused on the HSCT-TMA patients and will be summarized by OMS721 dose (4.0 mg/kg, 370 mg, and both doses combined). Atypical hemolytic uremic syndrome and TTP patients will be summarized separately by OMS721 dose.

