7.3. Study Endpoints

7.3.1. Primary Endpoints

The co-primary endpoints are:

- Safety as assessed by adverse events (AEs), vital signs, ECGs, and clinical laboratory tests (includes patients with HSCT-TMA, aHUS, and TTP)
- For HSCT-TMA patients, response to OMS721 treatment. A responder is defined as a patient with HSCT-TMA who demonstrates improvement in laboratory TMA markers (platelet count and LDH) and clinical benefit (either improvement in organ function or reduction in transfusion burden). The specific criteria are defined as follows:
 - Improvement in laboratory TMA markers:
 - Platelet count:
 - For patients with baseline platelet count $\leq 20,000/\mu\text{L}$:
 - Tripling of baseline platelet count
and
 - Post baseline platelet count $> 30,000/\mu\text{L}$
and
 - No platelet transfusions 2 days before and on the day of the platelet count collection
 - For patients with baseline platelet count $> 20,000/\mu\text{L}$
 - Increase in platelet count $\geq 50\%$
and
 - Post baseline platelet count $> 75,000/\mu\text{L}$
and
 - No platelet transfusions 2 days before and on the day of the platelet count collection
 - and**
 - LDH:
 - $\text{LDH} < 1.5 \times \text{upper limit of normal (ULN)}$
 - and**
 - Improvement in clinical status:
 - Improvement in organ function as evidenced by any of the following:
 - Improvement in renal function:

CONFIDENTIAL

No use, disclosure or reproduction outside of Omeros without prior written authorization

- Reduction of creatinine > 40%
- or
- Creatinine < ULN and reduction of creatinine > 20%
- or
- Discontinuation of renal replacement therapy (RRT)

or

- Improvement in pulmonary function:
 - Extubation and discontinuation of ventilator support
- or
- Discontinuation of non-invasive mechanical ventilation (continuous positive pressure ventilation)

or

- Improvement in neurological function:
 - Improvement in reversible neurological conditions (e.g., cessation of seizures)
- or
- Stabilization of irreversible neurological conditions (e.g., stability of neurological deficits following stroke without further deterioration or subsequent strokes)

or

- Improvement in gastrointestinal function (gastrointestinal HSCT-TMA will require diagnosis by tissue biopsy):
 - Improvement measured by improvement in the gastrointestinal measures in the Mount Sinai Acute GVHD International Consortium (MAGIC) criteria

or

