7.3.2. Secondary Endpoints

The secondary endpoints are to evaluate the following in patients with HSCT-TMA treated with OMS721:

- Duration of response, defined as the number of days from the first response date to the first relapse date

CONFIDENTIAL

No use, disclosure or reproduction outside of Omeros without prior written authorization

- 100-day survival, from the date of TMA diagnosis
- Overall survival, from the date of TMA diagnosis
- Freedom from platelet transfusion defined as no platelet transfusions for at least 4 weeks following the last platelet transfusion except for patients who died within 4 weeks of the last platelet transfusion (only evaluated in patients who had platelet transfusions in the 2 weeks prior to or on the first OMS721 dose date)
- Freedom from RBC transfusion defined as no RBC transfusions for at least 4 weeks following the last RBC transfusion except for patients who died within 4 weeks of the last RBC transfusion (only evaluated in patients who had RBC transfusions in the 2 weeks prior to or on the first OMS721 dose date)
- Change from baseline in platelet count (post baseline platelet counts without platelet transfusions 2 days before and on the day of the platelet count collection will be used) over time using central laboratory values
- Change from baseline in LDH over time using central laboratory values
- Change from baseline in haptoglobin over time using central laboratory values
- Change from baseline in Hgb (post baseline Hgb without RBC and whole blood transfusions 6 days before and on the day of the Hgb collection will be used) over time using central laboratory values
- Change from baseline in creatinine over time using central laboratory values
- The PK of multiple-dose administration of OMS721 (this will be assessed in patients with HSCT-TMA as well as patients with aHUS and TTP)
- The PD of multiple-dose administration of OMS721 (this will be assessed in patients with HSCT-TMA as well as patients with aHUS and TTP)
- The immunogenicity of multiple-dose administration of OMS721 (this will be assessed in patients with HSCT-TMA as well as patients with aHUS and TTP)

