13.2.1.1. Handling of Missing Data

Non-responder imputation will be used to handle missing data for the binary efficacy endpoints. Time-weighted average analysis and repeated measures models will be used to analyze the continuous secondary efficacy endpoints over time.

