2.5. Study Endpoint Baseline

In general, the baseline of a study endpoint is the last observation prior to the first study drug administration except for platelet count.

The baseline of a laboratory parameter will be based on the central laboratory values except for platelet count.

Platelet counts from the central laboratory are to be used in the calculation of baseline. If a central laboratory value is not available and its local laboratory value is available on the same collection date, the local laboratory value will be used. In addition, if there are at least 2 platelet count collections on the same date, the first one will be used.

Baseline platelet count is defined as the average of values obtained on different days in the week (including Day 1) prior to the first dose of OMS721. If more than 3 such values are available, then the 3 values that are most proximate to the first dose of OMS721 should be used. [Table 2](#) is an example of a baseline platelet count calculation.

Table 2: Example of Baseline Platelet Count Calculation

Study Day	Central Lab	Local Lab	Value to be used to Determine Baseline
-5	Yes	Yes	Not used
-4	Yes	Yes	Central lab
-3	No	Yes	Local lab
-2 (1 st)	No	Yes	Not used
-2 (2 nd)	Yes	No	Central lab
-2 (3 rd)	Yes	Yes	Not used

In addition, if at least 1 central laboratory value is used in the baseline calculation, the reference range of the central laboratory will be used to determine the toxicity grade according to National Cancer Institute (NCI) Common Terminology Criteria for Adverse Events (CTCAE). If the baseline value is calculated from local laboratory values only, then the reference range of the local laboratory will be used.

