3.2.5. Hematopoietic Stem Cell Transplant-Associated Thrombotic Microangiopathy History

HSCT history will be summarized with descriptive statistics by dose for the safety population:

- Underlying disease
- Donor source (related or unrelated)
- Time from HSCT to Day 1
- Graft-versus-host disease (Yes or No)
- Significant infection (Yes or No)
- Refractory primary disease or primary disease relapse (Yes or No)
- Graft failure or non-engraftment (Yes or No)
- Female-to-male transplant (Yes or No)
- Multiple organ TMA involvement (Yes or No)
- Mismatched donor (Yes or No)
- Neurological findings at baseline (Yes or No)
- Renal dysfunction at baseline (Creatinine > ULN, or spot urine protein $\geq 2+$ or > 30 mg/dL; Yes or No)

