4. PROTOCOL AND STATISTICAL ANALYSIS PLAN AMENDMENTS AND DEVIATIONS FROM THE PROTOCOL

SAP v1.1 incorporates changes made in Protocol Amendment [REDACTED]. These changes include the sample size of Stage 2 and the addition of Stage 3. The sample size determination was also clarified in SAP v1.1 and the statistical analyses remained the same. In addition, the dose of 4 mg/kg weekly for Stage 2 was selected based on the safety review of Stage 1 data.

SAP v2.0 incorporates changes made in Protocol Amendment [REDACTED]. The majority of the changes are due to the addition of the study endpoints and additional data collection for the HSCT-TMA patients.

REFERENCES

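### Baseline creatinine has two conflicting definitions, one of which includes four weeks of on-treatment values, and neither document says which one the renal response uses

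*Protocol*

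**What the plan says.** Protocol Section 13.2.1 takes the last pre-dose value as baseline and then makes two exceptions, platelet count and creatinine. For creatinine: "The baseline creatinine is defined as the maximum creatinine value between the diagnosis of TMA and 4 weeks after the first dose of OMS721". SAP Section 2.5 has one exception: "In general, the baseline of a study endpoint is the last observation prior to the first study drug administration except for platelet count". Creatinine therefore falls under the SAP's pre-dose rule, although that section never names it.

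The renal criteria (Protocol Section 7.3.1, SAP Section 2.1) ask for "Reduction of creatinine > 40" percent, or a fall of more than 20% to a value below ULN, or discontinuation of renal replacement therapy. Neither reduction criterion says what the fall is measured from. The analysis sections (Protocol 13.2.5.1, SAP 2.8.2.1) do not say either.

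Baseline creatinine also enters:
- the secondary endpoint "Change from baseline in creatinine over time using central laboratory values", for which Protocol Section 13.2.1.1 states: "Time-weighted average analysis and repeated measures models will be used to analyze the continuous secondary efficacy endpoints over time";
- the SAP subgroup and history variable that begins "Renal dysfunction at baseline (Creatinine > ULN, or spot urine protein".

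On precedence, Protocol Section 13.2 leaves the details to the SAP and adds: "A change to the data analysis methods described in the protocol will require a protocol amendment only if it alters a principal feature". SAP Section 4 does not mention creatinine. It says of version 2.0 only: "The majority of the changes are due to the addition of the study endpoints and additional data collection for the HSCT-TMA patients".

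**The concern.** Renal improvement alone satisfies the clinical half of the co-primary response, and it is the whole clinical half of the first alternative response. Its reference value is open, so the responder count depends on which document the programmer follows.

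The two rules are not neutral alternatives. The protocol's maximum includes up to four weeks of post-dose values. Taken from the same data, it can equal or exceed the last pre-dose value but never fall below it, so it can only ease the reduction criteria. No creatinine value through week 4 can exceed such a baseline. Worsening in that period cannot appear as worsening in the change-from-baseline analysis, and the mean change is negative even when nothing has changed. If the same rule were carried into the subgroup variable, a patient with normal pre-dose creatinine who rose above ULN on treatment would be classed as having renal dysfunction at baseline.

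The study is uncontrolled, Protocol Section 5.1 reports laboratory improvements already observed, and the interim analysis is meant to support a submission. The rule should therefore be fixed in writing before that lock.

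**Working it through.** **1. The plan's own figures.** Clopper-Pearson 95% intervals for n = 28 have widths from 12.34% to 38.71% (stated 12.3% to 38.7%). At 14/28 the interval is 30.65% to 69.35% (stated 30.6% to 69.4%). Both reproduce, and neither depends on the creatinine rule.

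**2. Decision threshold.** Efficacy is declared if the lower bound exceeds 15%. Eight of 28 responders give 13.2% and nine give 15.9%, so the rule needs nine. Near that count, one reclassified patient changes the conclusion.

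**3. Response with no net improvement (no variability assumption).** If a patient returns exactly to the pre-dose value, the apparent fall from the maximum is 1 − pre-dose/maximum.
- The fall exceeds 40% when maximum/pre-dose > 1/0.6 = 1.67.
- The fall exceeds 20% when maximum/pre-dose > 1/0.8 = 1.25. This route also needs the value to be below ULN.

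Example with assumed values: pre-dose 2.0, on-treatment peak 3.0, later 1.7 mg/dL. From pre-dose the fall is 1 − 1.7/2.0 = 15%, which fails >40%. From the maximum it is 1 − 1.7/3.0 = 43%, which passes.

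**4. Chance response with stable creatinine (illustrative).** The documents give no within-patient variability, so it is varied here. Assumptions:
- 20,000 patients per cell, lognormal values, no true change, day-to-day AR(1) correlation 0.8 and 0.9.
- Scheduled sampling: one screening value at Day −7, then Days 1, 8, 15, 22, 29, 36, 50 and 92. Weekly and daily sampling: Day −13 to Day 71.
- Protocol baseline: maximum through Day 29, with a qualifying value required to be post-dose and later than the maximum. SAP baseline: the Day 1 pre-dose value.

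Chance of meeting the >40% route, protocol baseline vs pre-dose baseline:

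| CV | Scheduled visits | Weekly | Daily |
|---|---|---|---|
| 5% | 0% vs 0% | – | – |
| 10% | 0.2–0.4% vs ≤0.1% | 0.4–0.7% vs 0.1% | 2–7% vs 0.2–0.5% |
| 15% | 9–13% vs 3–4% | – | 41–68% vs 7–11% |
| 20% | 31–40% vs 11–14% | 43–55% vs 14–17% | 77–95% vs 23–32% |

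(– = not tabulated.) For either creatinine route at scheduled visits and CV 10%, the result depends on the true level: 45–55% vs 18–21% at 0.9 × ULN, 14–17% vs 8–10% at 1.2 × ULN, and 0.2–0.3% vs 0.1% at 2 × ULN.

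A separate simulation used daily values for the maximum, the lowest of seven post-dose visits, correlation 0.8 to 0.95, and no requirement that the low value follow the maximum. For the >40% route, protocol vs pre-dose, it gave 0.3–1.4% vs under 0.1% at CV 10% and 34–74% vs 8–14% at CV 20%. The direction is the same.

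**5. Mean change with no true change.** At scheduled visits, Days 8–29, the protocol baseline gives about −5% to −6% (CV 5%), −10% to −11% (CV 10%) and −18% to −20% (CV 20%). The pre-dose baseline gives 0% to +4%.

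**6. Effect on the composite.** Excess = P(platelet and LDH met) × P(no other clinical route) × (difference in renal rate). Assume 0.5 × 0.5 = 0.25, independence, the >40% route and scheduled visits. At CV 20% the renal difference is 31 − 11 = 20 to 40 − 14 = 26 points. Then 0.25 × 20 = 5 and 0.25 × 26 = 6.5 points, or about 1.4 to 1.8 of 28 patients. With products from 0.09 to 0.42 in place of 0.25, the excess is about 2 to 11 points. At CV 10% it is under 0.1 point.

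**The case against.** The strongest reply is that the SAP governs. The protocol calls its statistical section an overview and defers to the SAP for detail, and SAP Section 2.5 is the section on endpoint baselines. A programmer working from it would use the pre-dose value, and the harm would never arise. That reading is plausible, but nothing in either document states it for a conflict. A baseline that feeds a co-primary endpoint is arguably a principal feature needing an amendment, and SAP Section 2.5 is worded as a general rule. The SAP's silence cannot safely be taken as a deliberate override either: SAP Section 1.1 still lists a renal-function secondary objective that Protocol Section 6.2 does not contain, so the two documents were not fully aligned.

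Several limits on size do stand:
- The simulated rates run from 0% to 95% across the assumed CVs and sampling schemes, so they show direction and possible size, not an estimate for this trial.
- HSCT-TMA entry requires creatinine to have doubled from before transplant, so a true level of 0.9 × ULN is possible but may not be typical.
- The subgroup variable is defined only in the SAP. Misclassification there requires the protocol rule to be carried across.
- Actual creatinine values are plotted and acute kidney injury is collected, so on-treatment worsening is hidden only in change from baseline.
- The improvements reported in Protocol Section 5.1 concern laboratory TMA markers, a term the response definition uses for platelet count and LDH. They do not show that creatinine data were reviewed.

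None of these removes the contradiction or the 1.67 and 1.25 multiples.

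**Conclusion.** The concern holds. The two baseline rules conflict, the response criteria name no reference value, and no text settles which rule applies. This follows from the documents alone, as do the one-way effect of the protocol rule and the multiples of 1.67 and 1.25. It needs correction before the interim lock because it reaches the co-primary response, the first alternative response and a secondary endpoint.

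The numerical size is conditional. It is negligible for the >40% route at scheduled visits with CV 10% or less. At CV 20% it is about 5 to 7 points on the composite under the assumptions in step 6. A shift of that size decides the 15% rule only when the count is near nine of 28.

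**What to change.** Before the interim database lock:
1. Delete the creatinine exception in Protocol Section 13.2.1, leaving platelet count as the only exception.
2. State in SAP Section 2.5 that baseline creatinine is the last pre-dose value for the renal response criteria, the creatinine change endpoint and the baseline renal-dysfunction subgroup.
3. If the protocol is not amended, list the departure in SAP Section 4.
4. Report any maximum-based result only as a labelled sensitivity analysis.

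A separate, secondary point: the evaluability review covers confounding in general but does not say whether creatinine drawn during renal replacement therapy counts. The SAP should state that such values are not evaluable for the two creatinine-reduction routes. The dates of therapy are already collected.

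The cost is one protocol sentence deleted and two SAP sentences added, with no new data. The renal response count may be lower.

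Two things remain. A pre-dose baseline does not remove the false positives that come from accepting any single qualifying value (the second figure in each pair above). SAP Section 2.5 also limits the creatinine baseline to central values, while response uses local and central values, so the SAP should say what applies when no central pre-dose value exists.
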